16. PRIVACY AND CONFIDENTIALITY OF SUBJECTS AND RESEARCH DATA

Assessment data collected for this study will be entered into REDCap. A unique study number will be assigned to each subject and all records pertaining to a given individual will be linked via this identification number. The databases will be password protected and access will be limited to relevant research personnel. All subject identification data (e.g., names, identification numbers, email addresses, telephone numbers, etc.) will be separated from the research data and stored securely on a URMC password-protected server, Box.com. Subject identification data will be used to contact enrolled subjects for their follow-up assessment appointment. All paper files (i.e., assessment forms, intervention notes, interview notes, etc.) will be stored in a locked file cabinet in the primary investigators' locked office in the Department of Psychiatry at URMC. Only IRB-approved investigators with a need for access will have access to subject data. As an added protection, NIH-funded studies are covered by a Federal Certificate of Confidentiality.

The assessment and intervention sessions will be video recorded on Zoom. Research personnel will use a licensed URMC Zoom account which protects and encrypts all audio, video, and screen-sharing data and supports HIPPA compliance. Subjects participating in the assessment and intervention sessions will be sent unique Zoom links for entering the Zoom meetings. Research personnel will use the waiting room feature to control subject access to the sessions and will lock the meetings after the subject joins the session. Following the sessions, the recordings will be directly uploaded to password-protected drives on Box.com for secure storage. The recordings will be accessible only by IRB-approved study personnel at URMC.

Publications or presentations resulting from this study will report only cumulative data or descriptions certain to maintain subjects' anonymity. Lastly, to minimize social and legal risks, this study contains a Certificate of Confidentiality to protect subjects' information. An explanation of the Certificate of Confidentiality is included in the informed consent form

All data collected as part of this study will be stored for a minimum of 3 years after the completion of the study.

17. DATA AND SAFETY MONITORING PLAN

Safety Monitoring: Given that this study presents no more than minimal risk, data and safety monitoring will be the responsibility of the study PI, in consultation with the PIs' mentoring team. Individual subject data will be monitored by the PI and study personnel over the course of the study to identify any subjects who may need additional support. Alcohol use, and symptoms of post-traumatic stress disorder (PTSD), depression, suicidal risk, anxiety, and insomnia will be assessed at screening, baseline, and one-month follow-up assessments. If at any time a subject is identified by study personnel or the PI as having a serious psychiatric or alcohol use problem that requires immediate and intensive treatment (i.e., danger to self or others), this concern will immediately be reported to the PI and the PI's primary mentor, who will provide support, referral, and bridging to appropriate treatment options for stabilization. Should a subject present at a study session under the influence of drugs or alcohol, study personnel will be trained to discontinue the session, reschedule the session for a later date, and work with the subject to ensure they are in a safe place (i.e., at home, with family or friends, etc.). Should a subject communicate distress and intent to withdraw from the study, the PI will provide the subject with a list of

Deaf treatment resources to help the individual locate possible treatment options in their area.

Study personnel will be trained contact 911 in the event of a dangerous situation. The PI will also be available for on-call phone consultation for less urgent clinical crises. The PI will intervene if at any time a subject's distress cannot be contained or in cases where anyone appears truly unsafe (e.g., suicidal intent, threatening harm, or other unsafe behavior). Although it is anticipated that this reaction is highly unlikely, if concerns of subject safety arise (i.e., intent to harm oneself or others) then, to promote safety, confidentiality will not be maintained, and appropriate professionals will be informed. During crisis situations, clinical information may be provided to other clinicians (or family members) in order to facilitate appropriate treatment and minimize the risks of self-harm or harm to others. The PI and her primary mentor are licensed psychologists; thus, in the event that a subject is found to pose imminent harm to themselves or others, the PI in collaboration with her mentoring team will implement any actions required by the law with regard to individuals who are determined to pose imminent harm to themselves or others.

Evaluation of Adverse Events: An adverse event (AE) is any negative reaction or untoward event which does not necessarily have a causal relationship with the study procedures. An AE can be any unfavorable or unintended experience (i.e., distress, worsening of symptoms, suicidal ideation, etc.) occurring during the study period, whether or not it is related to the study procedures. This includes any newly occurring event or previous condition that has increased in severity or frequency since the start of the study period.

Cognitive Behavioral Therapy for Treatment Seeking (CBT-TS) is a low-risk intervention focused on connecting individuals in need of treatment to professional services. Therefore, AEs related to the intervention are not expected. However, this study will include a clinical population with moderate to severe symptoms of anxiety, depression, trauma, sleep disturbance, and alcohol use. It is possible that subjects will experiencing a worsening of symptoms, suicidal thoughts or behaviors, acute intoxication, withdrawal, and/or hospitalization during the study period. We will monitor, collect, and report AEs through our screening and baseline assessments, intervention sessions, and follow-up assessments. All AEs will be reported to the study PI and her mentoring team. Unexpected adverse events, or any negative experiences, the specificity or severity of which are not consistent with the risk information provided in the protocol, will also be monitored and reported to the study PI and her mentoring team.

The PI, in collaboration with her mentoring team, will distinguish a serious adverse event (SAE) from a non-serious adverse event (AE) and provide attributions (causality and severity). If needed, we will consult with the University of Rochester Medical Center (URMC) IRB for assistance and clarification in this process. A serious adverse event is defined as any event that is serious (i.e., death, hospitalization, and life-threatening events), unanticipated, and study related.

Adverse Event Reporting: SAEs that are associated with the study and occur while a subject is on the study until 14 days after the date the subject goes off study must be reported in writing to the URMC IRB within 2 working days. SAEs that are both **unexpected fatal or life-threatening events** must be reported immediately to the IRB. SAEs will also be reported to and University of Rochester Clinical and Translational Science Institute (UR CTSI) KL2 program directors. The PI and her mentoring team, will develop follow-up plans for any SAEs and unresolved unexpected adverse events in collaboration with the URMC IRB.

Data Handling Considerations:

Data Collection, Entry, and Storage:

Subjects will provide data to their best knowledge by responding to items on self-report questionnaires at screening, baseline and post-intervention. Subjects' responses will be recorded on paper forms and manually entered in REDCap. Study personnel will administer the screening, baseline, and follow-up assessments to the subjects on Zoom via ASL and record their responses on paper forms. This data will be manually transferred to REDCap after the assessment sessions. The intervention sessions will be video recorded on Zoom and stored on Box.com. During the intervention sessions, the interventionist will record notes of the treatment beliefs discussed in session, the alternative beliefs developed by the subject, and the subject's short-term action plan. This data will be manually entered into REDCap after the session. The semi-structured interviews during the follow-up assessment will be video recorded on Zoom and stored on Box.com. Study personnel will manually record subjects' responses to the structured questions and enter this data into REDCap after the session. All paper copies of forms, intervention notes, or interview responses, will be stored in a locked cabinet in the PI's locked office in the Department of Psychiatry at URMC.

Data entered into REDCap will be cross-checked by visual audit of forms, then checked through programmatic error checks prior to data analysis. Once data collection is complete, REDCap provides an automated export procedure for data download. Every effort will be made to reduce attrition and obtain follow-up data including flexible scheduling options, immediate scheduling of follow-up sessions, frequent appointment reminders, and follow-up contacts after missed sessions.

Missing Data

Every effort will be made to facilitate the subjects' completion of questionnaires and comprehensive collection of data. If there are missing data, reasons for missing data will be recorded, tabulated, and reported. We will use the information about missing data when assessing feasibility.

The assumptions underlying all statistical analyses will be thoroughly checked using appropriate graphical and numerical methods. If there are serious violations of distribution assumptions such as normality, appropriate nonparametric methods will be attempted. If outliers or influential data are detected, the accuracy of the data will be investigated. If no errors are found, analyses may be repeated after removing these cases to evaluate their impact on the results. However, the final analyses will include these data points. SPSS and Stata will be used for the statistical analyses.

Data Security

Every effort will be made to protect subjects' confidentiality. Only IRB approved study personnel with a need will have access to identifying information (i.e., subject names, contact information), which will be kept separate from subject data on a URMC password protected server (Box.com). Paper data will be stored in a locked file cabinet in the PI's locked office in the Department of Psychiatry at URMC. All intervention sessions and the follow-up assessment session will be video recorded on Zoom. The Zoom recording will be directly uploaded to a password protected server (Box.com) for secure storage.

All other study data will be entered into REDCap, a HIPPA compliant, secure, web-based application designed exclusively to support data capture for research studies.

REDCap is hosted locally by URMC and employs user authentication and role-based security. The REDCap application resides in an isolated secure network segment designed for personal health information, personal identifiable information, and other types of regulated data.

Data will be exported to SPSS and Stata for analyses. All analytic files will be stripped of personal identifiers. Only CITI-trained personnel with appropriate authorization and relevant project need will be allowed data access. Individual data will not be available for release.

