11. RISKS TO SUBJECTS

The proposed study procedures pose minimal risks to subjects. The information below that describes the risks associated with the study interventions was taken from the IRB approved protocol and consent form.

- a. **Assessment sessions (i.e., screening, baseline, and follow-up):** For the assessment sessions, the risks are as follow: mild reactions of distress or fatigue, identification of suicide ideation, invasion of privacy, or breach to confidentiality (if safety issues are detected). Subjects are not required to answer any questions posed during the study

and they may withdrawal from the study at any time without consequences. Subjects may request breaks if needed during the study or may request to stop at any time. Study personnel have specialized training in working with Deaf individuals who have behavioral health problems and are capable of providing support as needed. All of the assessment measures and the assessment procedures were safely used in my URMC IRB approved pilot study with Deaf individuals. No sustained negative effects from the assessments are expected, but negative outcomes cannot be ruled out. There is a slight risk that research data files might be compromised and obtained or viewed by unauthorized persons. Our procedures for protecting against such risks are described below.

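### The SAE definition also requires an event to be unanticipated and study related, so an unrelated death or hospitalization is classed as non-serious

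*Combined protocol and SAP*

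**What the plan says.** Everything on this point is in Section 17 (Data and Safety Monitoring Plan), apart from the risk list in Section 11.

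- **Adverse events.** Under Evaluation of Adverse Events, an AE is any untoward event in the study period, whatever its cause. The section does not expect AEs caused by the intervention. Because the population is symptomatic, it does list as possible "suicidal thoughts or behaviors, acute intoxication, withdrawal, and/or hospitalization during the study period".
- **Serious adverse events.** An SAE is "any event that is serious (i.e., death, hospitalization, and life-threatening events), unanticipated, and study related".
- **Sorting.** The PI, with the mentoring team, "will distinguish a serious adverse event (SAE) from a non-serious adverse event (AE) and provide attributions (causality and severity". They may consult the IRB if needed. No third class is named.
- **Unexpected events.** These are events "the specificity or severity of which are not consistent with the risk information provided in the protocol". Section 11 lists mainly distress, fatigue, identification of suicidal ideation, loss of privacy or confidentiality, and difficulty obtaining services. It adds: "No sustained negative effects from the assessments are expected, but negative outcomes cannot be ruled out", with a similar sentence for the intervention sessions.
- **Reporting.** All AEs go to the PI and mentoring team. The IRB receives a written report within 2 working days of "SAEs that are associated with the study and occur while a subject is on the study" or in the 14 days after the subject goes off study. SAEs that are "unexpected fatal or life-threatening events" go to the IRB immediately. In addition, "SAEs will also be reported to and University of Rochester Clinical and Translational Science Institute (UR CTSI) KL2 program directors". Follow-up plans are made with the IRB for SAEs and for unresolved unexpected AEs.

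Section 18 (Data Analysis Plan) describes no safety summary.

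**The concern.** Whether an event is serious is a matter of its outcome. Whether it was foreseen, and whether the study caused it, are separate judgments. Section 17 folds all three into one label. Its only other class is called non-serious, so the label can misdescribe what happened to the subject.

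The relatedness condition matters most. The plan does not expect intervention-related AEs, so few events are likely to meet it. Relatedness is judged by the PI and mentoring team in a single-arm study, with no comparison group to inform the judgment. The population, meanwhile, is one in which the plan itself regards hospitalization as possible.

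Two things are at stake. Serious events that miss the label are not sent to the KL2 program directors and are not assured of an SAE follow-up plan. And Section 12 says the pilot should support moving to a randomized trial. A statement that no SAEs occurred would be read as no deaths, life-threatening events or hospitalizations, when it would mean only that none was both unanticipated and study related.

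**Working it through.** The plan states no SAE rate, so there is no figure to reproduce. The check is mainly logical, with an illustration of scale.

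**1. Classification.** Take an event with one of the three listed outcomes (death, life-threatening event, hospitalization) and apply the definition, treating unanticipated and unexpected as the same test.

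| Unanticipated | Study related | Class as written | Class by outcome alone | Assured route as written |
|---|---|---|---|---|
| yes | yes | SAE | SAE | PI and mentoring team, IRB, KL2 directors |
| yes | no | non-serious AE | SAE | PI and mentoring team; IRB follow-up plan if unresolved |
| no | yes | non-serious AE | SAE | PI and mentoring team |
| no | no | non-serious AE | SAE | PI and mentoring team |

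One of four combinations is an SAE as written; by outcome alone, all four are. This counts logical cases and is not a frequency.

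**2. The unanticipated condition.** Section 17 names hospitalization as possible in this population, which suggests it is anticipated. It also tests unexpectedness against the protocol's risk information. If that means Section 11, hospitalization is not listed and would be unanticipated. The same admission can be classified either way, depending on which section is used. Expectedness decides the label, yet the attributions to be recorded are causality and severity only.

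**3. Fit with the reporting paragraph.** The written-report rule is limited to SAEs associated with the study, and the immediate-report rule to unexpected ones. Under the definition every SAE is already both, so neither limit does any work. They make sense only if unrelated or expected SAEs can exist, which the definition rules out.

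**4. Scale.** Input from Section 5: n = 45. The per-subject risk p of any listed outcome on study is not in the documents, so it is assumed at 1%, 2% and 5%. Expected events = n × p; chance of at least one = 1 − (1 − p)^45.

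- p = 0.01: expected 0.45; chance 0.364
- p = 0.02: expected 0.90; chance 0.597
- p = 0.05: expected 2.25; chance 0.901

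If every such event is judged unrelated, the count is 0/45 in all three cases.

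Now let a share q of serious events meet all three conditions. The chance of zero SAEs despite at least one serious event is (1 − pq)^45 − (1 − p)^45.

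- p = 0.02: 0.511 for q = 0.10; 0.395 for q = 0.25
- p = 0.05: 0.699 for q = 0.10; 0.468 for q = 0.25

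**5. What 0/45 would support.** The one-sided 95% upper bound is 1 − 0.05^(1/45) = 6.4%; the two-sided exact bound is 1 − 0.025^(1/45) = 7.9%. Under the current definition these bounds apply only to unanticipated, study-related serious events, not to all serious events.

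**The case against.** The strongest reply is that little is lost in practice. AEs are defined and collected regardless of cause, their causality and severity are recorded, and all reach the PI and mentoring team. Section 17 also requires immediate notice to the PI and primary mentor of a psychiatric or alcohol problem needing immediate, intensive treatment. The IRB can be consulted on hard classifications. The non-serious label is an inference, since no sentence applies it to an unrelated death, and the reporting limits suggest the authors may use the term SAE more broadly than they define it. No aim, endpoint or estimate is affected. Section 18 plans no SAE table, and the study is described as minimal risk.

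Much of this stands, and it limits the importance of the point. Events are not lost, and a statement of zero SAEs is foreseeable rather than planned. The event rates are assumptions. Because Section 15 replaces withdrawn and removed subjects, the number exposed may also exceed 45. The unanticipated condition is open to argument: Section 17 is itself protocol text and may count as risk information. And the KL2 sentence carries no filter, so a corrected definition would largely settle what goes to the directors.

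None of it repairs the definition. Consulting the IRB is optional. The inference to the non-serious label rests on the definition and a two-class rule in the same subsection, and nothing elsewhere broadens either. If the authors do mean something broader, the text should say so.

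**Conclusion.** The point holds, and the definition should be corrected. On relatedness the conclusion is firm: as written, a death, life-threatening event or hospitalization judged unrelated is a non-serious AE. On expectedness it is arguable, because the plan does not settle which text is the reference for foreseen risks.

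One of the four combinations a serious event can have is labelled an SAE. How often the other three would occur is unknown. Under the assumed 1% to 5% risk, about 0.45 to 2.25 serious events would be expected among 45 subjects, and zero SAEs could be recorded despite them. The practical gain is modest: correct classification, a complete tally and clear KL2 notification. Written IRB reporting would not become faster or wider, since that rule is already limited to study-associated SAEs.

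**What to change.** In Section 17:

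1. Define an SAE by the section's own outcome list (death, life-threatening event, hospitalization), regardless of expectedness or relatedness.
2. Record relatedness and expectedness as separate assessments. Add expectedness to the existing causality and severity attributions, and name the sections that serve as the reference risk information.
3. Reconcile the reporting paragraph with the new definition, so that association with the study and unexpectedness act only as filters for expedited IRB reporting. This must accompany item 1. The immediate-report sentence has no relatedness limit of its own, so changing the definition alone would bring unexpected deaths and life-threatening events judged unrelated under it.
4. Confirm which SAEs go to the KL2 program directors.
5. Tabulate all SAEs, related or not, in the final report.

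The cost is a reworded definition, one added assessment field and an edited reporting paragraph. A few more events would be listed as SAEs, about 0 to 2 expected under the assumed risks. With item 3 in place, the expedited IRB trigger need not change.

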1. PURPOSE OF STUDY

The purpose of the current study is to assess the acceptability and feasibility of a Zoom-based intervention, Cognitive Behavioral Therapy for Treatment Seeking (CBT-TS) to improve professional treatment-seeking among Deaf¹ adults with mental health and/or alcohol use problems. This study is a Stage 1A intervention refinement study (Onken et al., 2014) consisting of a single-arm open pilot trial that will recruit 45 Deaf subjects, aged 18 years or older, with significant symptoms of alcohol use disorder (AUD), post-traumatic stress disorder (PTSD), depression, anxiety, and/or insomnia, who are not currently engaged in treatment. Subjects will be recruited online from across the United States (U.S.) for this remote study. All subjects will complete a baseline assessment of their behavioral health symptoms, perceptions towards treatment, and intent to seek treatment prior to engaging in the CBT-TS intervention. The primary clinical outcome, assessed at one-month follow-up, will be whether subjects scheduled professional treatment. Secondary outcomes include changes in subjects' perceptions towards treatment and intentions to seek treatment. During the one-month follow-up assessment (i.e., at the completion of their participation in the study) subjects will also complete a client satisfaction survey and a semi-structured interview with open-ended questions to provide feedback about the CBT-TS intervention. All study activities will be conducted via Zoom. The specific aims include the following:

Aim 1: Assess the acceptability and feasibility of CBT-TS for Deaf Individuals using recruitment and retention data and qualitative and quantitative subject feedback.

Aim 2: Generate a preliminary estimate of the effect size for CBT-TS for Deaf Individuals using one-month follow-up assessments to assess changes in subjects' utilization of professional treatment services, perceptions of treatment, and intentions to seek treatment.

Aim 3: Refine CBT-TS for Deaf individuals intervention using qualitative and quantitative data from the study to enhance the acceptability and potential effectiveness of CBT-TS for Deaf individuals.

[figure not shown]

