All subjects will be offered an optional second session with the interventionist. The second session will consist of a 60-minute appointment focused on providing practical assistance to identify available treatment options in the subject's area, scheduling treatment sessions, and problem-solving barriers to treatment (e.g., accommodations). Subjects will be informed that the second session must be scheduled within three weeks of completing the first session. The interventionist will immediately offer to schedule a second session at the end of the first intervention session. If subjects do not immediately schedule a second session, study personnel will check in with subjects 10 days after their first intervention session to see if they would like to schedule a second session. If three weeks pass without completing the second session, subjects will proceed with the follow-up assessment at the one-month mark after their first intervention session. If a second session is scheduled, subjects will be contacted for the follow-up assessment one month after completing their second intervention session. The intervention sessions will be video recorded on Zoom and stored on Box.com, a password-protected secure server hosted at URMC.

Follow-up Assessment: One month after their last intervention session, study personnel will contact the subjects to schedule a follow-up assessment session on Zoom. The follow-up assessment will follow the same general procedures as the screening and baseline assessments. During the follow-up assessment, study personnel will re-administer the behavioral health measures and the D-PASS from the baseline assessment, along with a validated treatment utilization survey which will assess subjects' use of 12 treatment services, their reasons for seeking or not seeking treatment, and any barriers they experienced through a series of structured questions.

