Lastly, to obtain quantitative and qualitative feedback about CBT-TS for Deaf Individuals, subjects will complete the Client Satisfaction Questionnaire (CSQ-8) and a semi-structured interview including several open-ended questions about the intervention measure, content, materials, and delivery, including its appropriateness for use with the Deaf community, the acceptability of the techniques, and the usefulness of the content and materials. As these questions will be asked one month after the subjects complete their intervention session, study personnel will provide descriptions of each of the intervention procedures and show subjects the intervention materials again to refresh their memory of their experience as they provide feedback on the intervention. The interviewer will take notes of the subjects' responses to the structured questions and enter this data into REDCap after the session. The paper copies of the subjects' responses will be stored in a locked cabinet in the PI's locked office in the Department of Psychiatry at URMC.

The follow-up assessment will be video recorded on Zoom. The recordings will be stored on Box.com.

Sharing Results: Subjects will be given the opportunity to receive a summary of the results from the trial. If interested, subjects will be asked to check a box at the end of the written consent form to give the research team permission to contact them after the completion of the study. The research team will prepare a brief written and signed summary of the main findings from the trial and email this information to the interested subjects.

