15. SUBJECT WITHDRAWALS

Subjects will be advised during the consent process that they have the right to withdraw from the study at any time without penalty. If a subject chooses to withdraw from the study the data collected up until their withdrawal will be used for data analyses. Subjects may be removed from the study if they experience significant distress during the screening and baseline assessments or the intervention session. Withdrawn and removed subjects will be replaced.

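### No fallback is specified for obtaining the yes/no primary clinical outcome from subjects who do not attend the one-month Zoom follow-up

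*Combined protocol and SAP*

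**What the plan says.** Section 1 defines the endpoint and its timing: "The primary clinical outcome, assessed at one-month follow-up, will be whether subjects scheduled professional treatment". It also fixes the mode: "All study activities will be conducted via Zoom".

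Section 9 (Follow-up Assessment) says that, one month after the last intervention session, "study personnel will contact the subjects to schedule a follow-up assessment session on Zoom". In that session the symptom measures and the D-PASS are repeated, "along with a validated treatment utilization survey which will assess subjects' use of 12 treatment services". The CSQ-8 and a semi-structured interview come last.

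Section 17 (Data Collection, Entry, and Storage) lists ways to limit attrition and secure follow-up data, among them flexible scheduling and "frequent appointment reminders, and follow-up contacts after missed sessions". It does not describe what those contacts ask. Under Missing Data it says: "If there are missing data, reasons for missing data will be recorded, tabulated, and reported". Section 15 adds that for a subject who withdraws "the data collected up until their withdrawal will be used for data analyses", and that withdrawn and removed subjects are replaced.

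Section 18 (Aim 2) reports the proportion who schedule treatment within one month of the intervention. It does not say how a subject without follow-up enters that proportion.

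**The concern.** The outcome is a single fact that a subject could give in one short exchange. The only described route to it is an appointment that also carries the symptom scales, the D-PASS, the utilization survey, the CSQ-8 and an interview. A subject who never attends that appointment has no described route to an outcome, even though staff expect to be in touch after a missed session.

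Attendance may well be related to scheduling. Subjects who took no step may avoid the visit, and so may subjects now busy with treatment. The direction is unknown, and a single-arm trial has no comparison group that might reveal it. The proportion is Aim 2's preliminary estimate of efficacy, and Section 12 says the results are meant to support a randomized trial.

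**Working it through.** **Is there another source for the outcome?**

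- Follow-up assessment (Section 9): yes. The utilization survey is the closest instrument.
- Intervention notes (Sections 9 and 17): these record beliefs, alternative beliefs and the action plan, not scheduled appointments.
- Ten-day check-in (Section 9): described only as an offer of the second session.
- Contacts after missed sessions (Section 17): content not stated.
- Records check, or a short form by email, text or videophone: none described.

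So the follow-up assessment is the only described source.

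**How much could it matter?** The plan has no figure of its own to reproduce: 45 is given without a precision target or an expected follow-up rate.

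Inputs:

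- N = 45 (Section 5).
- An illustrative scheduling rate near 31%. This is the share connected to treatment in the investigator's preliminary data (Section 2), used only to set the scale.
- Number without follow-up, m = 5, 9 or 14 of 45 (11%, 20%, 31%): assumed.
- Share recovered by a brief contact, 25% to 75%: assumed.

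Formulas: with x scheduled among n = 45 − m observed, the worst case is x/45, the best case is (x + m)/45, and the width is m/45. Intervals are exact (Clopper-Pearson) 95%.

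| m | Observed | 95% interval | Worst case | Best case | Width (points) | Width if about half recovered |
|---|---|---|---|---|---|---|
| 0 | 14/45 = 31.1% | 18.2–46.6% | 31.1% | 31.1% | 0 | – |
| 5 | 12/40 = 30.0% | 16.6–46.5% | 26.7% | 37.8% | 11.1 | 3/45 = 6.7 |
| 9 | 11/36 = 30.6% | 16.3–48.1% | 24.4% | 44.4% | 20.0 | 5/45 = 11.1 |
| 14 | 10/31 = 32.3% | 16.7–51.4% | 22.2% | 53.3% | 31.1 | 7/45 = 15.6 |

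Each unresolved subject adds 1/45 = 2.2 points, whatever the scheduling rate. With 25% to 75% recovered, 9 missing become 7 to 2 unresolved, a width of 15.6 to 4.4 points.

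Precision suffers little: the interval is 28.5 points wide with all 45 observed and 31.8 with 9 missing. The main cost is possible selection bias.

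The denominator of 45 is itself an assumption. If withdrawn subjects are replaced and also kept in the analysis, the total exceeds 45 and each missing answer counts slightly less.

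**The case against.** A reader might infer three stronger things. The documents support none of them.

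1. That the contacts after missed sessions do not ask about scheduling. Section 17 is silent on their content and lists them among efforts to secure follow-up data. Silence does not establish that the question is left out.
2. That the whole session must be completed. Section 9 describes the survey before the CSQ-8 and interview, so a session cut short could still yield the outcome, and Section 15 keeps data gathered before withdrawal.
3. That every non-attender is an avoidable loss. Rebooking, flexible scheduling and the $75 follow-up payment (Section 14) should bring some subjects back. Others will be unreachable or will decline whatever is asked.

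It can also be said that this is a Stage 1A pilot without a hypothesis test, that follow-up completion is itself an Aim 1 result, and that a 20-point worst-to-best range is narrower than the 28.5-point sampling interval at full enrolment. All of this is correct and limits the weight of the point. But sampling error and missing-outcome uncertainty are separate and both apply. Tabulating reasons for missing data serves feasibility without recovering any outcome. Replacement restores the count but does not remove selection.

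A brief contact has problems of its own. An early no is not a one-month no. A loosely worded question would not match the survey. Email and text raise privacy issues, and written English loses the ASL support that Section 9 provides. These bear on how the fallback is written.

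**Conclusion.** The point holds in a limited form. The one-month Zoom follow-up is the only described source of the primary clinical outcome, no minimal-data fallback is specified for subjects who do not attend, and the content of the planned missed-session contacts is not stated. The Aim 2 proportion may therefore describe mainly those who attended.

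The size cannot be fixed from the documents, which give neither an attrition rate nor a recovery rate. Under the assumed 9 of 45 missing, the range is 20.0 points, or 11.1 if 4 of the 9 are recovered. Whether any bias arises, and in which direction, is unknown. The change is worth making because staff already plan the contacts and already hold email and videophone details (Section 11).

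**What to change.** In Section 17, with matching changes to the Zoom-only statement in Section 1 and to Section 9, state the following.

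- **Who and when.** A subject who received session 1 and has not completed the follow-up assessment after rebooking attempts is asked one question at the missed-session contact, at or after the one-month mark.
- **What.** Was an appointment for professional mental health or alcohol treatment (the services covered by the utilization survey) scheduled, and on what date? The date allows classification against the same one-month window as Section 18.
- **How.** By videophone in ASL where possible. Email or text is used only with the subject's permission, in line with the safeguard in Section 8, and with IRB approval.
- **Early stopping.** Ask permission to put this single question at one month. An answer given at the time of stopping counts only if it is a dated yes; an early no stays unresolved.
- **Analysis.** Flag these answers by mode and timing, and report the Section 18 proportion with and without them.

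The cost is one question within contacts already planned, REDCap fields for answer, date, mode and timing, and a small IRB amendment. The downside is a shorter, less detailed form of collection for a few subjects, which the flags and the paired report make visible.
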